## 3.0 Background

- 3.1 Pediatric appendicitis represents the most common pediatric abdominal surgical disease with the highest incidence found in children aged ten to 19 years old (1). The diagnosis of appendicitis commonly consists of a thorough history, physical exam and laboratory evaluation along with diagnostic imaging. With both a high sensitivity and specificity, CT scan remains the most commonly used imaging modality for diagnosis (2). With reports in the literature showing the adverse effects of radiation exposure in children from computed tomography (CT) imaging (3, 4), alternative methods to diagnose acute appendicitis have been applied including Magnetic Resonance Imaging (MRI) (4) and ultrasound (US). MRI eliminates ionizing radiation when compared to CT however, its widespread use is limited due to its high cost, limited availability and the potential need for sedation in young children. Trans-abdominal ultrasound is widely available and also eliminates ionizing radiation but is user dependent. The utilization of CEUS to enhance the diagnostic capabilities for appendicitis is a novel alternative to CT imaging.
- 3.2 A recent report in the literature demonstrates the effective use of CEUS to evaluate blunt solid organ injuries in children with abdominal trauma (5).

In Europe, CEUS using SonoVue, the European brand-name for Lumason, has been used clinically for more than a decade, reported mainly in adults. Valentino, et al. published results of a prospective study performed in Italy comparing the sensitivity and specificity of ultrasound and CEUS to abdominal/pelvis CT with IV contrast. A total of 27 patients were prospectively studied and they found CEUS to have a 92.9% sensitivity, 100% specificity, 100% positive predictive value (PPV) and 93.8% negative predictive value (NPV) compared to CT (6). Valentino published a subsequent study of 133 adult trauma patients with blunt abdominal solid organ injury on CT who underwent CEUS and found 96.4% sensitivity, 98% specificity, 98.8% PPV and 94% NPV (7) compared to CT.

Lumason is now FDA-approved for echocardiography in adults, characterization of liver lesions in both the adult and pediatric population, and vesicoureteral reflux in pediatrics.

- 3.3 The potential use of CEUS to diagnose pediatric appendicitis remains unknown. The goal of this trial is to determine the utility of

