## 4.0 Study Endpoints

4.1 The primary endpoint is the proportion of patients for whom the appendix is enhanced by CEUS when using the same diagnostic criteria as gray scale ultrasound. Lumason will be considered effective if the sensitivity of grayscale ultrasound is enhanced in more than 50% of images as determined by the blinded interpreting pediatric radiologist.

Secondary endpoints include:

- Utility of CEUS in making a definitive diagnosis of acute appendicitis
- Utility of CEUS in decreasing rates of CT scan utilization
- Negative appendectomy rates

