5.3 N/A

## 6.0 Procedures Involved

- 6.1 This will be a single-center non-randomized trial that will add to our institution's current diagnostic algorithm one CEUS to subjects whom are clinically suspicious for acute appendicitis. Currently, a gray-scale abdominal ultrasound is performed to help establish the diagnosis. When the results of the gray-scale abdominal ultrasound are inconclusive, the treating physician may choose to refer the patient for a CT scan in order to establish a definitive diagnosis. Our study does not look to alter that process.
- 6.2 For those who consent to study participation, we propose obtaining a CEUS after the initial gray-scale ultrasound. Once the initial ultrasound is complete, the contrast Lumason® (sulfur hexafluoride lipid type-A microspheres) will be administered through an already existing IV catheter by an MD, RN or a radiology technologist trained and certified to administer the Lumason® contrast agent, and

an abdominal scan will be completed. The patient will then continue with standard of care treatment per his treating physician. The CEUS image will be read at a future time by a CMH radiologist blinded to the results of the gray scale ultrasound and CT if one was obtained as these will be used for comparison.

6.3

- Lumason will be administered by radiology personnel (radiologist, US technologist, or Sedation RN). Subjects will be monitored during the entirety of the procedure. Once the study procedure has been completed, patients will continue to go through the standard of care process and return to the ED (Emergency Department) or floor while they await the results of their gray-scale ultrasound and CT, if one was obtained. ED/ floor staff will continue to monitor patients for any adverse events.
- Lumason (sulfur hexafluoride lipid-type A microspheres) is the investigational product. The recommended dose of Lumason for children is 0.03 mL/kg up to a maximum dose of 2.4mL injected into a peripheral intravenous catheter. See individualization of dose below.

1. Follow the Lumason injection with a flush of 5 ml of 0.9% Sodium Chloride Injection, USP.
2. The maximum total dose for children as listed in the package insert should not exceed 2.4 mL in any 10-minute period. For this study, over any 10-minute period we intend to administer the approved dose of 0.03 mL/kg up to a maximum of 2.4 mL.

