## 11.0 Inclusion and Exclusion Criteria

### Inclusion Criteria

- Present to Children's Mercy Adele Hall campus with a clinical concern for acute appendicitis
- Age 8 through 17 years
- seen between IRB approval date and 12/31/2020
- Has had an IV catheter placed as part of their standard of care

Exclusion Criteria

- Known cardiac abnormality
- Pulmonary hypertension
- Known sensitivity to sulfur hexafluoride, polyethylene glycol 4000, distearoylphosphatidylcholine (DSPC), dipalmitoylphosphatidylglycerol sodium (DPPG-Na), or palmitic acid
- Does not have an IV catheter placed
- Unable to roll over
- Unable to assent
- Pregnant
- Lactating
- Received an ultrasound image from an OSH

*11.1 These patients will be excluded from the study*

- Adults unable to consent
- Pregnant women
- Prisoners
- Wards of the state

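### The 4.1 success rule is one-sided: it judges Lumason on enhancement or sensitivity alone, and no endpoint counts CEUS false positives

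*Protocol*

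**What the plan says.** Protocol section 4.1 defines the primary endpoint as "the proportion of patients for whom the appendix is enhanced by CEUS when using the same diagnostic criteria as gray scale ultrasound". The success criterion follows: "Lumason will be considered effective if the sensitivity of grayscale ultrasound is enhanced in more than 50% of images", as judged by the blinded radiologist. The secondary endpoints in section 4.0 are "Utility of CEUS in making a definitive diagnosis of acute appendicitis", "Utility of CEUS in decreasing rates of CT scan utilization" and negative appendectomy rates. None names specificity, positive predictive value or false-positive CEUS reads.

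Other sections bear on this:

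- **Section 2.1:** the objective is to improve the diagnosis of appendicitis.
- **Section 11.0:** children enter on suspicion: "Present to Children's Mercy Adele Hall campus with a clinical concern for acute appendicitis".
- **Section 3.0:** imaging is judged on both kinds of error: "With both a high sensitivity and specificity, CT scan remains the most commonly used imaging modality for diagnosis". The CEUS studies cited there are summarised by sensitivity, specificity, PPV and NPV.
- **Sections 6.1 and 6.2:** of the usual work-up the protocol says "Our study does not look to alter that process". The CEUS is read afterwards, blinded to gray scale and CT, which serve as comparators.
- **Section 6.4:** ultrasound, CEUS, CT, pathology and operative findings are collected.
- **Section 20.1:** operative findings are correlated with the gray-scale read, in children who meet appendicitis criteria. The CEUS read is not mentioned in that correlation.

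**The concern.** A diagnostic test can err in two directions, and the stated criterion looks at one. Some enrolled children will not have appendicitis, and a false alarm in such a child counts against Lumason nowhere in section 4.0. A trial run exactly as written could declare Lumason effective for diagnosis while specificity is worse than with gray scale.

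This is separate from the inconsistency between patients and images as the unit in 4.1. It would remain with one result per child.

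**Working it through.** **Step 1. Does any endpoint register a false-positive CEUS call?**

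- *Primary endpoint and success rule:* no reference standard enters the definition, and only enhancement or sensitivity is named. Sensitivity is a property of diseased children, so calls in the others drop out.
- *Definitive diagnosis:* nothing requires the diagnosis to be correct.
- *CT utilization:* under 6.1 and 6.2 the CEUS read does not decide who has a CT, so a wrong call leaves no trace here.
- *Negative appendectomy rates:* this counts operations. They are decided without the CEUS read, so the rate describes standard care.
- *Section 20.1 correlation:* limited to children meeting appendicitis criteria, and tied to the gray-scale read.

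The answer is no for all five. The protocol gives no power calculation or assumed rate behind the 50% threshold, so there is no planned figure to reproduce.

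**Step 2. What does a false positive do to the result?** That depends on the meaning of 'enhanced', which the protocol does not define.

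*(a) Better image of the appendix.* The diagnostic call is not scored. A false positive is ignored.

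*(b) Better sensitivity.* A lower reading threshold raises sensitivity and costs specificity, and the rule sees only the first. No figure is attached here, because 4.1 does not say how a gain in sensitivity becomes a proportion of images.

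*(c) CEUS meets the gray-scale criteria for appendicitis.* The endpoint is then a test-positive rate:

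rate = prevalence × sensitivity + (1 − prevalence) × (1 − specificity)

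Prevalence among enrolled children is not given. The 375 diagnoses a year in 13.2 come without the number of suspected cases. I assume 30% to 60%, with sensitivity 90%. At 40% prevalence:

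- specificity 100%: 0.4 × 0.9 + 0.6 × 0 = 36%
- specificity 90%: 0.36 + 0.6 × 0.10 = 42%
- specificity 75%: 0.36 + 0.6 × 0.25 = 51%

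The range over prevalence, by the same formula:

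| Prevalence | Spec. 100% | Spec. 90% | Spec. 75% |
|---|---|---|---|
| 30% | 27% | 34% | 44.5% |
| 40% | 36% | 42% | 51% |
| 60% | 54% | 58% | 64% |

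The direction is the same in every row: each point of specificity lost adds (1 − prevalence) points to the endpoint. Whether the 50% line is crossed depends on the assumed prevalence. These are expected rates. With 250 children and one result each, a true rate of 51% gives at least 126 successes in about 60% of trials.

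**Step 3. Can specificity be estimated with the planned enrolment?** At 40% prevalence there are 250 × 0.6 = 150 children without appendicitis. For a paired difference near zero and a discordant proportion d (assumed 10% to 20%), the 95% half-width is about 1.96 × √(d/150). This gives 5.1 points at d = 0.10 and 7.2 points at d = 0.20. Over 30% to 60% prevalence (175 to 100 such children) the range is 1.96 × √(0.10/175) = 4.7 to 1.96 × √(0.20/100) = 8.8 points. No extra children are needed for a useful estimate.

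**The case against.** The best counter-argument is that 'enhanced' may mean no more than a better picture. Section 4.1 speaks of the appendix being enhanced, and 18.1 describes the possible benefit as better image quality. On that reading a well-shown normal appendix is a success, and over-calling is not rewarded. This stands, and it limits the point: false positives are ignored on every reading and rewarded on one. The reference to the same diagnostic criteria lends that one reading some support but does not establish it.

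A reader might infer that a perfect CEUS must fail whenever half or fewer of the children have appendicitis, or that passing requires specificity below some threshold. The documents do not support either as a statement about this trial. Both need reading (c) and an assumed prevalence, and both treat expected rates as outcomes.

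Second, the statistical analysis plan is not shown and may report specificity. That is fair, and the absence of a specificity analysis is not the point. The only stated success criterion sits in the protocol and is one-sided there.

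Third, 18.1 suggests that better images might inform treating providers, so CEUS over-calls might reach the negative appendectomy rate. Sections 6.1 and 6.2 describe a later read and an unaltered pathway. Even otherwise, only over-calls that led to surgery would be counted.

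Finally, the root problem may be called one of definition. In part it is, and the two should be settled together. But defining 'enhanced' as image quality or as sensitivity would still leave specificity out.

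**Conclusion.** The concern holds in this form: the 4.1 rule is one-sided, and nothing in section 4.0 counts a wrong positive CEUS call. The trial could therefore support a claim of effectiveness for diagnosis without showing that specificity was preserved. That conclusion rests on the text alone.

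The stronger statement, that over-calling moves the result toward success, is conditional on 'enhanced' meaning a positive read by the gray-scale criteria. The size of that effect (36% to 51% as specificity falls from 100% to 75%) rests on an assumed 40% prevalence and 90% sensitivity, and serves as illustration only.

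This is a cheap improvement that should be made. Its importance depends partly on how 'enhanced' is defined, so it does not rank as a fatal flaw in its own right.

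**What to change.** Amend 4.1, together with the definition of 'enhanced', as follows:

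1. Assign every child a final diagnosis: pathology or operative findings if operated, chart outcome or CT if not.
2. Score each child's blinded CEUS read and gray-scale read as correct or not against it. Treat uninterpretable or inconclusive reads alike for both tests, for example as not correct. The rule for inconclusive gray-scale reads matters because they are the situation named in the 2.2 hypothesis.
3. Report sensitivity in children with appendicitis and specificity in children without it, each as a paired CEUS minus gray-scale difference with a 95% CI.
4. Allow the word effective only when sensitivity improves without a loss of specificity beyond a limit fixed before the first CEUS read. The sponsor should choose and justify that limit; the two-sided scoring is the core of the change.
5. Require the definitive-diagnosis endpoint to count correct diagnoses only.

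Cost: no added enrolment, and imaging, pathology and operative findings are already collected (6.4), with standard-care chart data available (10.0). The extra work is chart review for unoperated children, since 20.1 plans follow-up only for those who meet appendicitis criteria. Verification in unoperated children will be imperfect, and that limitation should be stated. The success claim becomes harder to meet.

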## 2.0 Objectives

- 2.1 The main objective of this study is to determine the efficacy of Contrast Enhanced Ultrasound (CEUS) in improving the diagnoses of acute appendicitis in children.
- 2.2 We hypothesize that CEUS can be used effectively to make a definitive diagnosis when gray-scale ultrasound is inconclusive.

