**13.0 Local Number of Subjects**

*13.1 This study will enroll 250 subjects. Assuming an accrual rate of 15-20 subjects per month, we estimate it will take 12-15 months to complete enrollment.*

*13.2 Based on prior data, approximately 375 children are diagnosed with appendicitis at our institution per year. We plan to screen up to 750 potential subjects for eligibility over the course of the study.*

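### The fixed 50% success bar in Section 4.1 does not use the gray-scale result, so it either fails to show improvement over gray scale or has a ceiling set by gray scale's own success rate, depending on what enhanced means

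*Protocol*

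**What the plan says.** Section 2.1 sets the aim as to "determine the efficacy of Contrast Enhanced Ultrasound (CEUS) in improving the diagnoses of acute appendicitis in children". Section 2.2 narrows this to a subgroup: "We hypothesize that CEUS can be used effectively to make a definitive diagnosis when gray-scale ultrasound is inconclusive".

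Section 4.1 defines the primary endpoint as "the proportion of patients for whom the appendix is enhanced by CEUS when using the same diagnostic criteria as gray scale ultrasound". The next sentence gives the decision rule: "Lumason will be considered effective if the sensitivity of grayscale ultrasound is enhanced in more than 50% of images". The judgement belongs to the blinded interpreting radiologist.

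Section 6.2 has every participant undergo gray scale and then CEUS. The CEUS reader is blinded to gray scale and to any CT, "as these will be used for comparison". Section 20.1 repeats the blinding to the gray-scale reads.

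Enrolment (Section 11.0) is open to children who "Present to Children's Mercy Adele Hall campus with a clinical concern for acute appendicitis" and is not limited to inconclusive scans. Section 13.1 gives the size: "This study will enroll 250 subjects".

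The protocol states no gray-scale success rate and no reason for choosing 50%. Gray scale has no stated role in the decision rule.

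**The concern.** A claim of improvement needs a comparison with what gray scale achieved in the same children. The rule in 4.1 is a single proportion against a fixed number. Its two sentences also describe different quantities. The endpoint sentence can be read as the share of children in whom CEUS meets the criteria. The decision sentence is worded as a gain over gray scale.

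This matters because the rule produces the trial's only statement that Lumason is or is not effective. The same data can give opposite verdicts under the two readings, and under either one the verdict can run against the objective in 2.1.

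**Working it through.** **Inputs.** Bar above 50% (4.1). N = 250 (13.1), all assumed evaluable, with one result per child. A pass therefore needs at least 126 of 250, since 125/250 is exactly 50.0%. The gray-scale success rate g is not in the protocol, so it is an assumption and is varied. There is no derivation of the 50% to reproduce.

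A gain is gray scale no, CEUS yes. A loss is gray scale yes, CEUS no.

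**Reading 1: CEUS-alone rate.** The CEUS count is gray-scale successes + gains - losses. Take 150 gray-scale successes (60%), 20 gains and 40 losses:

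- CEUS successes = 150 + 20 - 40 = 130, or 52%. The rule says effective.
- Paired difference d = (20 - 40)/250 = -0.08.
- SE = sqrt[(gains + losses)/250 - d²]/sqrt(250) = sqrt(0.24 - 0.0064)/15.81 = 0.0306.
- 95% CI = -0.08 ± 1.96 × 0.0306, that is -14.0 to -2.0 points. Exact McNemar p = 0.013.

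More generally, a true CEUS rate of 55% passes with probability 93.6% (exact binomial, at least 126 of 250), whatever gray scale's rate is.

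**Reading 2: yes/no gain.** Gains can occur only among gray-scale failures, so the proportion is at most 1 - g. The share of failures that CEUS must convert is 126/[250(1 - g)]:

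| Assumed g | Gray-scale failures | Share to convert |
|---|---|---|
| 20% | 200 | 63% |
| 30% | 175 | 72% |
| 40% | 150 | 84% |
| 45% | 137.5 | 92% |
| 50% | 125 | not possible (126 needed) |

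Here g is the rate observed in the enrolled children. If g is instead the true rate, a perfect CEUS passes with probability 99.9% at g = 40%, 93.6% at 45%, 47.5% at 50%, 4.9% at 55% and 0.06% at 60%.

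Example with g = 50%, 110 gains and no losses: CEUS succeeds in (125 + 110)/250 = 94% against 50%. The paired gain is 44 points (SE = sqrt(0.44 - 0.1936)/15.81 = 0.0314; 95% CI 38 to 50). The proportion with a gain is 110/250 = 44%, so the rule says not effective.

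A pass under Reading 2 does mean net improvement: 126 gains leave at most 250 - 126 = 124 possible losses.

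**The two readings on the same data.**

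| Data | Reading 1 | Reading 2 |
|---|---|---|
| CEUS 8 points worse | 52%, passes | 20/250 = 8%, fails |
| CEUS 44 points better | 94%, passes | 44%, fails |

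Reading 1 gives the wrong answer in the first row and Reading 2 in the second.

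**The case against.** Several points on the other side are sound.

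- A reader might infer that one bar both fails a perfect CEUS and passes a CEUS worse than gray scale. No single reading does this. On the CEUS-alone reading a perfect CEUS scores 100%. On the gain reading a CEUS worse on the same criterion cannot reach 126 gains.
- It is also tempting to say that neither reading measures improvement, or that losses never count. Passing on the gain reading does imply a net gain, and each loss does lower the CEUS-alone rate.
- The decision sentence is worded as a gain, so the CEUS-alone reading leans on the endpoint sentence. Against that, a reader blinded to gray scale can directly judge only the CEUS image.
- The 1 - g ceiling depends on yes/no coding and on an unstated g. If enhanced were a graded judgement of image quality, a scan on which gray scale already succeeded could still count and the ceiling would go. Section 4.1 defines no such grading.
- The problem is not independent of the population. Among children with inconclusive gray scale (2.2), g is 0 on a definitive-diagnosis criterion. The two readings then coincide and both faults vanish. But 4.1 does not restrict the denominator, and Section 11.0 enrols all suspected cases.

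An unseen SAP may specify a paired test, and Section 6.2 intends a comparison. The protocol nevertheless fixes the effectiveness rule itself, and that rule makes no use of the comparison.

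**Conclusion.** The point holds in limited form. As written and applied to all enrolled children, the rule in 4.1 can return a verdict contrary to the objective, and which error is possible depends on a definition the protocol leaves open. On the CEUS-alone reading the error is a false claim of effectiveness. On the gain reading it is a missed benefit: the required conversion rises from 63% to 92% of gray-scale failures as g goes from 20% to 45%, and the bar is out of reach from 50%.

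The sizes assume 250 evaluable children, yes/no scoring and illustrative gray-scale rates. The documents do not show that g is 50% or more at this site, so they do not support saying that the bar is in fact unreachable. The change should be made before the data are read.

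**What to change.** In Section 4.1, define one yes/no outcome per child, on the same criterion, for the gray-scale report and for the blinded CEUS read. Report gains, losses and the paired difference with its 95% CI, with McNemar's test. Call CEUS effective if the lower limit exceeds zero, or exceeds a gain that the sponsor states in advance if any gain above zero is too lenient. Keep the overall proportion enhanced as a descriptive figure.

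Alternatively, keep the 50% bar but apply it only to children whose gray-scale scan was inconclusive, with definitive diagnosis as the criterion. The protocol does not say how many there will be. Precision would be lower than with all 250, and losses could not be seen.

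**Cost.** Protocol wording, consistent yes/no coding of the gray-scale reports, and one paired analysis of the ultrasound and CEUS findings that Section 6.4 already collects. No added children or scans are needed. In simulation with 250 children, a 10-point net gain would be shown with probability of about 96%, 84% and 72% at 20%, 30% and 40% discordant pairs.

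**Downsides.** A net gain may look less favourable than a simple percentage. The comparison mixes reader with modality, because gray scale comes from the clinical report and CEUS from a separate radiologist. Meeting the criterion is not the same as a correct diagnosis, so the result should be read alongside pathology, CT and operative findings to avoid counting false positives as diagnostic gains.

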3. The maximum total dose for children as listed in the package insert should not exceed 4.8 mL in any one patient during the full time on study. In this study, we intend to administer a total dose in any one patient during the full time on study of 0.06 mL/kg with a maximal dose of 4.8 mL.

6.4 Data extracted from the electronic medical record will be entered into a secure REDCap database and stored in a password protected file on the CMH network. A master list containing only the assigned study ID and linking MRN will be kept in a separate REDCap instrument. All electronic files will be kept on the secure password-protected computers of the research staff and principal investigator.

Data points to be collected include the following: demographics, findings on radiology imaging (US, CEUS, and CT if applicable),

pathology, intraoperative findings, other/ comments. Reports of headache, nausea, altered taste, injection site reaction, feeling hot/ flushed, chest pain, or dizziness will also be recorded.

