17.3 N/A

17.4 N/A

17.5 N/A

## 18.0 Potential Benefits to Subjects

18.1 There is some possibility of potential benefit to subjects participating in this research. Although Lumason is not yet approved for use in diagnosing appendicitis, it is possible that the improved quality of US images produced will provide better information to providers treating these patients. It is also possible that the improved quality imaging could result in incidental findings, such as abdominal anomalies other than appendicitis. If such anomalies are found, the investigator could recommend to parents to follow up with appropriate services.

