## 20.0 Data Management and Confidentiality

20.1 The captured CEUS images will be evaluated by a single Children's Mercy Hospital pediatric radiologist to determine and establish a pattern compared to the standard gray scale ultrasound report. This radiologist will be blinded to the final reads from the gray scale reports. For the children who meet the criteria of appendicitis, they will be followed post-operatively to confirm and correlate the intra-operative findings with the gray scale read.

Descriptive analysis of demographics and patient-level data will be performed using STATA. Direct comparisons will be made with parametric or nonparametric measures depending on the distribution of the data.

- 20.2 This study will be made up of a convenience sampling of children presenting to the CMH Adele Hall emergency department with concerns for appendicitis. Enrollment will consist of up to 250 participants.
- 20.3 All data will be entered into a REDCap database that is accessible only to researchers named on the study. Data will be stored on the CMH secure network. The list of chart identifiers which meet inclusion criteria along with dates of birth will be maintained separately from data that will be used for analysis. Each chart will be reviewed by research staff and data entered directly into the research records. The researchers alone will have full access to the data; we will assign a study ID to the medical records in order that we can reference our information during the course of our research. A master list linking Study ID to MRN, Name and other identifiers will be kept separately from the study data, and accessible only to the study team.
- 20.4 N/A
- 20.5 All data will be entered into a REDCap database that is accessible only to researchers named on the study. Data will be stored on the CMH secure network. The list of chart identifiers which meet inclusion criteria along with dates of birth will be maintained separately from data that will be used for analysis. Each chart will be reviewed by research staff and data entered directly into the research records. The researchers alone will have full access to the data; we will assign a study ID to the medical records in order that we can reference our information during the course of our research. A master list linking Study ID to MRN and other identifiers will be kept separately from the study data, and accessible only to the study team.

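### Protocol 4.1 states its only success rule on gray-scale sensitivity rather than on the primary endpoint, and the rule cannot be applied as written

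*Protocol*

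**What the plan says.** Protocol 4.1 has two consecutive sentences on the primary endpoint. The first defines it as the "proportion of patients for whom the appendix is enhanced by CEUS when using the same diagnostic criteria as gray scale ultrasound". The second gives the success criterion: Lumason is effective if "the sensitivity of grayscale ultrasound is enhanced in more than 50% of images as determined by the blinded interpreting pediatric radiologist". No other efficacy criterion appears in the protocol.

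Three other places describe the reading and the comparison:

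- Section 6.2 has the CEUS image read at a later time by a radiologist "blinded to the results of the gray scale ultrasound and CT if one was obtained as these will be used for comparison".
- Section 20.1 has a single radiologist evaluate the CEUS images "to determine and establish a pattern compared to the standard gray scale ultrasound report". It continues: "This radiologist will be blinded to the final reads from the gray scale reports".
- Section 20.1 also says that children who meet the criteria for appendicitis are "followed post-operatively to confirm and correlate the intra-operative findings with the gray scale read". The CEUS read is not named there.

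**The concern.** The endpoint sentence concerns the appendix as shown by CEUS. The success sentence concerns the accuracy of the other test, gray-scale ultrasound. These are different attributes, and the second cannot be scored image by image. Since this sentence alone decides whether Lumason is called effective, whoever applies it must first replace it with something else, and the replacements do not all lead to the same verdict.

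A smaller concern is that 20.1 describes the radiologist's evaluation in terms of a comparison with reports that the same radiologist may not see. The comparison is evidently intended, but nobody is assigned to make it.

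**Working it through.** There is no planned figure to reproduce. The protocol derives neither the 50% threshold nor the sample size of 250, and it gives no expected sensitivity or enhancement rate. The check is a comparison of the text, followed by bounds that show what each reading does.

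**Step 1. The two sentences of 4.1 side by side**

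| | Endpoint sentence | Success sentence |
|---|---|---|
| Attribute | appendix enhanced by CEUS | sensitivity of gray-scale ultrasound |
| Counted in | patients | images |
| Judged by | not stated | the blinded radiologist |

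Sensitivity = (patients with disease whom the test calls positive) / (all patients with disease by the reference standard). It belongs to a group of patients. Section 3.2 uses the word in this technical sense when it reports the cited trauma studies against CT. A single image has no sensitivity, so one cannot count the images in which sensitivity rose.

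**Step 2. Reading A: *enhanced* means a case newly detected by CEUS**

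Let Se be gray-scale sensitivity. CEUS can newly detect only cases that gray scale missed, so

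newly detected share of confirmed cases ≤ 1 − Se.

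- Se = 60%: at most 40%
- Se = 75%: at most 25%
- Se = 90%: at most 10%

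A share above 50% requires Se below 50%.

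An illustration with assumed counts: 125 confirmed cases, of which gray scale detects 94 (75.2%). CEUS gains 25 and loses 6, so it detects 94 + 25 − 6 = 113 (90.4%).

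- Paired gain: (25 − 6)/125 = 19/125 = 15.2 points
- SE = √(31 − 19²/125)/125 = 0.0424, giving a 95% CI of 6.9 to 23.5 points
- Exact McNemar test (25 of 31 discordant pairs): p = 0.0009
- Newly detected share: 25/125 = 20%. If CEUS found all 31 missed cases it would be 31/125 = 24.8%.

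A clear gain in sensitivity therefore fails a 50% rule. With all 250 scanned patients as denominator the share is lower still (25/250 = 10%).

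**Step 3. Reading B: *enhanced* means the appendix is seen on CEUS**

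The smallest count above 50% of 250 is 126 (126/250 = 50.4%). If CEUS shows exactly the appendices that gray scale had already shown, and these number at least 126, the rule passes although no patient gained anything.

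**Step 4. Who compares**

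Section 6.2 withholds gray scale and CT from the reader because they are the comparators. That points to a blinded read first and a comparison later. Section 20.1 puts the comparison into the description of the radiologist's evaluation and then blinds that radiologist. Section 4.1 leaves the determination to the blinded reader. No passage names the person who sets the two reads against each other, or the time at which this happens.

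**The case against.** Several points on the other side have force.

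- **Blinding.** A reader might infer that the radiologist has been given an impossible task. The documents do not support that. Section 6.2 fits an ordinary design (blinded read, then comparison), and the phrase in 20.1 can state the purpose of the evaluation. What stands is a wording conflict and an unassigned comparison.
- **Patients versus images.** It is tempting to argue that counting images could reverse a verdict based on patients. That would need unequal image counts per patient, which the protocol does not describe. Section 6.1 adds one CEUS and 6.2 speaks of a single CEUS image. The difference in unit is minor; the difference in attribute is the defect.
- **Meaning of *enhanced*.** For a contrast agent, an enhanced appendix may simply be one that shows visible contrast enhancement, which a blinded reader can judge from CEUS alone. On that reading the endpoint sentence does not conflict with the blinding, and defining *enhanced* only by pairing with gray scale would replace the endpoint. This is accepted, and the fix leaves both meanings open.
- **Denominator.** One might infer that only patients with an inconclusive gray-scale scan should count, from hypothesis 2.2. That hypothesis matches the secondary endpoint on definitive diagnosis. The plain denominator of 4.1 is all patients scanned.
- **Role of an SAP.** An SAP may exist and may define *enhanced*, so it is not established that the choice would be made after the data are seen. But an SAP that drops the reference to sensitivity overrides the protocol's success sentence, so the correction belongs in 4.1.

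**Conclusion.** The point holds. The success sentence of 4.1 names an attribute that differs from the endpoint and that no single image can have, so the trial's only efficacy rule cannot be applied as written. That conclusion rests on the text alone.

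The size cannot be measured, because the protocol gives no expected rates. The bounds show only that the reading matters. Under reading A the rule cannot be met once gray-scale sensitivity is 50% or more. Under reading B it can be met at 126 of 250 with no gain over gray scale. The 15.2-point example uses assumed counts, and reading A is one possible interpretation rather than a rule that the protocol states.

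The blinding issue is secondary: 20.1 needs clarifying, but the design is workable.

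**What to change.** **Section 4.1.** Remove the references to gray-scale sensitivity and to images. State the rule on the endpoint's own attribute and unit: effective if the appendix is enhanced in more than 50% of patients who undergo CEUS. In the same sentence, fix one meaning of *enhanced* before reads are unblinded:

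1. a finding that the blinded reader makes from CEUS alone, in which case the conclusion is limited to visualisation and makes no claim of improvement over gray scale; or
2. an improvement over gray scale, derived by pairing the locked CEUS read with the gray-scale report. In that case, check that the threshold is attainable, since only patients whose gray-scale result leaves room for improvement can count.

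**Section 20.1.** State that the blinded radiologist records the CEUS read alone, that the comparison with gray scale follows once that read is locked, and who makes it.

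**If sensitivity is really meant.** Replace the 50% threshold with a paired difference in sensitivity between CEUS and gray scale in confirmed appendicitis, and extend the operative correlation in 20.1 to the CEUS read. Note the direction of bias: restricting to operated children tends to favour gray scale, because gray scale guides care and the later-read CEUS does not, so cases missed by gray scale are more likely to be left out.

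**Cost.** Protocol wording only, with no extra patients or readers, and possibly a narrower conclusion.
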